#### 7.2 Blinding

Due to the objectives of the study, treatment group allocation will not be known to investigators, research staff, or patients. The operating surgeon will be informed which method of fascial closure will be undertaken. As such, these individuals will be excluded from collecting outcome data. Upon consenting to proceed with the study, Access to the randomisation code will be strictly controlled and the study blind will be broken on completion of the clinical study and after the study database has been locked.

#### 7.3 Data collection method

Participants will be randomised to one of the three groups and will be provided a participant identification number on the day of their surgical procedure after consenting to proceed with the study. Subsequent to this, a chart review will be used to gather demographic information on participants, including age, gravida and para status, number of previous Caesarean sections, medical and surgical history, medication list, body mass index, and any obstetrical complications during the pregnancy. Participant's e-mails will be collected and saved in a separate document to maintain confidentiality.

Subsequent to this, participants will be e-mailed a link at each given time parameter to fill in their questionnaires which is a modified MD Anderson Brief Pain Inventory as a secure Google Docs Form (post-operative day #1 and 2, and at 2, 6 and 10 weeks post-operatively). As the participant's only identification is their participant identification number, this maintains participant confidentiality.

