## **PROTOCOL SYNOPSIS**

TITLE	Evaluation of the impact of fascial closure technique on post- operative pain in patients undergoing Pfannenstiel incision for Caesarean Section: A Randomised Trial
SPONSOR	DAN Women and Babies Unit, Sunnybrook Health Sciences Centre
FUNDING	DAN Women and Babies Unit, Sunnybrook Health Sciences Centre
ORGANISATION	
NUMBER OF SITES	1
RATIONALE	Caesarean sections are the most commonly performed surgical procedure throughout the world. Within the Canadian population, approximately one-third of all deliveries occur via Caesarean section. Chronic pain post-operatively has been identified as an issue that a large proportion of patients suffer with. As a result, a variety of surgical techniques have been undertaken, with some being compared to ascertain the reason for this chronic pain. One method which has been observed is related to the fascial layer and associated pain related to this layer. Whilst the abdominal fascia plays an integral role in ensuring the abdominal contents remain in situ. A variety of methods have been employed and studied to ensure the integrity of the fascial layer to reduce the risk of dehiscence, but no studies undertaken to date have evaluated the method of fascial closure and their effect on post-operative pain.
STUDY DESIGN	Randomised, double-blind, three-arm trial
PRIMARY OBJECTIVES	1. Analgesia use
	2. Pain score between three groups
NUMBER OF SUBJECTS	350
SUBJECT SELECTION	Inclusion Criteria:
	- Women aged 18-60 years
	- Women with singleton pregnancy
	
 
Patient undergoing elective lower segment Caesarean section via a Pfannenstiel Incision
 

	- Use of Regional Anaesthesia (epidural or spinal anaesthesia)
	Exclusion Criteria:
	- Multiple pregnancy
	
 
Patient undergoing non-elective Caesarean section
 

	- Caesarean section through midline laparotomy incision
	
 
Patients undergoing Caesarean section under General Anaesthesia
 

	- History of chronic pain
	
 
History of chronic pain
 
History of post-operative complications (haematoma, abscess,
 

	- History of post-operative complications (naematoma, abscess, dehiscence, re-operation)

	· · · · · · · · · · · · · · · · · · ·									
ARMS AND	Participants will be blinded to which method of fascial closure will									
INTERVENTIONS	be undertaken at the time of their surgery.									
	1. Single suture, knot above rectus fascia									

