	2. Two sutures, knots above rectus fascia									
	3. Two sutures, buried knots below rectus fascia									
DURATION OF SUBJECT	Subjects will be enrolled in the study for 10 weeks.									
PARTICIPATION AND	Screening: 1 day									
DURATION OF STUDY	Treatment: 1-2 days (subjects will be admitted to hospital)									
	Follow-up: 10 weeks									
	The total duration of subject recruitment time is 6 months, with									
	subsequent follow-up over a 10-week period after initial									
	recruitment.									
EFFICACY										
EVALUATIONS										
PRIMARY ENDPOINT	1. Analgesia use in first 72-hour period post-operatively.									
	2. Pain score questionnaire results over 10-week post-operative									
	period.									
STATISTICS										
Primary Analysis Plan	Statistical analysis will be undertaken using IMB ® SPSS ® Statistical									
	Software ver. 26 to undertake a two-sided T-test comparing group									
	1 vs. 2 and group 1 vs. 3 to assess for statistical significance in									
	analgesia use and pain scores.									
Rationale for Number	Based on a power of 80% at an alpha of 0.05, we estimate a 15%									
of Subjects	reduction in pain scores. As a result, we require a total of 255									
	subjects in this study. Given an estimated drop-out rate of 35%, we									
	aim to recruit a total of 350 participants.									
	In addition, sub-group analysis will be undertaken comparing pain									
	scores between primary and repeat Caesarean sections. Based on									
	the same power of 80% at an alpha of 0.05, with an estimation of a									
	15% difference in pain scores, we require a total of 140 subjects for									
	this sub-group analysis.									
L										

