## 2 STUDY RATIONALE

LSCS are the most commonly performed surgical procedures worldwide. Given that much of the development of surgical approaches for trainees is based on the centre at which they are trained, there is no standardised approach which offers superiority as it relates to specific steps in the procedure. Given these issues, the notion of an evidence-based approach to fascial closure which minimises post-operative pain would be superior as it relates to the patient's return to normal activities, duration of analgesia use and overall quality of life. It is for this reason we aim to undertake this study comparing three methods of rectus fascia closure during LSCS at our unit to ascertain if there is an impact on patient's post-operative pain.

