## 9 DATA SAFETY MONITORING

Sunnybrook Health Sciences Centre Data Safety Monitoring Board (DSMB) will establish a Data Monitoring Committee (DMC) to review data related to safety and efficacy, to ensure scientific validity and merit of the study, according to Sunnybrook Health Sciences Centre Data Safety Monitoring Board Operations Manual and a DMC Charter to be established for this protocol.

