#### **12.5** Investigator Responsibilities

By being involved in this study, the Investigators, as part of the Research Team, agrees to:

- 1. Conduct the study in accordance with the protocol and only make changes after notifying the Sponsor (or designee), except when to protect the safety, rights or welfare of subjects.
- 2. Personally conduct or supervise the study (or investigation).
- 3. Ensure that the requirements relating to obtaining informed consent and IRB review and approval meet federal guidelines, as stated in § 21 CFR, parts 50 and 56.
- 4. Report to the Sponsor or designee any AEs that occur in the course of the study, in accordance with §21 CFR 312.64.
- 5. Ensure that all associates, colleagues and employees assisting in the conduct of the study are informed about their obligations in meeting the above commitments.
- 6. Maintain adequate and accurate records in accordance with §21 CFR 312.62 and to make those records available for inspection with the Sponsor (or designee).
- 7. Ensure that an IRB that complies with the requirements of §21 CFR part 56 will be responsible for initial and continuing review and approval of the clinical study.
- 8. Promptly report to the IRB and the Sponsor (or designee) all changes in the research activity and all unanticipated problems involving risks to subjects or others.
- 9. Seek IRB approval before any changes are made in the research study, except when necessary to eliminate hazards to the patients/subjects.
- 10. Comply with all other requirements regarding the obligations of clinical investigators and all other pertinent requirements listed in § 21 CFR part 312.

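### The plan describes no systematic collection and no by-arm reporting of wound complications after closure, and 5.4 and the synopsis disagree on whether women who have them stay in

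*Combined protocol and SAP*

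**What the plan says.** **The risk and the aim.** The synopsis rationale says closure methods have been used and studied to "ensure the integrity of the fascial layer to reduce the risk of dehiscence". Section 2 argues that "an evidence-based approach to fascial closure which minimises post-operative pain would be superior"; the sentence goes on to limit this to recovery of normal activity, time on analgesia and quality of life.

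**Endpoints.** The synopsis lists two: "Analgesia use in first 72-hour period post-operatively" and "Pain score questionnaire results over 10-week post-operative" (over the whole follow-up). The secondary objective in 3.2 is also about pain, in primary against repeat Caesareans. Section 10.2 plans t-tests for these and contains no safety analysis.

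**Data collection.** Under 7.3, "a chart review will be used to gather demographic information on participants". The items are baseline ones, and the only complications among them are those of the current pregnancy. Section 10.1 gives a similar list. Follow-up is the e-mailed questionnaire on days 1 and 2 and at weeks 2, 6 and 10. Appendix C asks about pain, its interference with daily life, and pain relief.

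**Safety text.** Section 9 sets up a committee "to review data related to safety and efficacy, to ensure scientific validity and merit of the study". Section 12.2 requires serious adverse experiences to go to the ethics board. Section 12.5 asks investigators to "Report to the Sponsor or designee any AEs that occur in the course of the study".

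**Exclusions.** Section 5.4 item 6 names post-operative haematoma, abscess, dehiscence and re-operation. The synopsis names the same four but as a history of them.

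**The concern.** The arms differ in the number of sutures and the position of the knots, and what is being closed is the layer whose failure the synopsis names as the reason for studying closure. A reader choosing between techniques will want to know whether less pain came with more, fewer or similar wound problems. As described, the trial could answer only from events that happened to be reported. Such reports may be incomplete, and not necessarily to the same degree in each arm.

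The exclusion wording adds a second problem. Section 7.3 places randomisation on the day of surgery, so a complication of that operation necessarily comes after randomisation. If 5.4 item 6 were applied as worded, women with these events would leave the comparison because of something the allocated closure might have influenced.

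**Working it through.** The plan states no complication rate and no safety sample size, so there is no figure to reproduce. The check has two parts.

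**1. Could any described data stream capture the events?**

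| Stream | Covers | Elicits wound events after closure? |
|---|---|---|
| Chart review (7.3, 10.1) | Demographics, history, current pregnancy | No |
| Questionnaire (7.3, Appendix C) | Pain, interference, pain relief | No item; three opening answers of No end the form |
| Study visits | None described after the 1–2 day admission | No |
| AE and SAE duties (12.2, 12.5) | Events that become known | Passive; no event definition, window or elicitation |
| Monitoring committee (9) | Reviews safety data | Generates none itself; no safety variables named |
| Analysis (10.2) | Pain and analgesia | No comparison by arm |

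**2. What would collecting them give?**

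Inputs from 5.2: 85 per arm required; 350 recruited, so 350 / 3 = 116.7 per arm. The documents give no complication rate, so 0.5%, 1%, 2% and 5% are assumed.

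*Zero events in an arm.* The one-sided 95% upper limit is 1 − 0.05^(1/n).
- n = 117: 1 − 0.05^(1/117) = 2.5%.
- n = 85: 1 − 0.05^(1/85) = 3.5%.

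*Power for a doubling between two arms.* Two-sided alpha 0.05, normal approximation: power = Φ[(d − 1.96·se0) / se1], with d = p2 − p1, p̄ the mean of p1 and p2, se0 = √(2p̄(1 − p̄)/n) and se1 = √((p1(1 − p1) + p2(1 − p2))/n).

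Worked case, 2% against 4% with n = 116: d = 0.02; se0 = √(2 × 0.03 × 0.97 / 116) = 0.0224; se1 = √((0.0196 + 0.0384) / 116) = 0.0224. Then (0.02 − 0.0439) / 0.0224 = −1.07, and Φ(−1.07) = 14%.

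| Assumed rate, doubled in the other arm | Expected events in the lower arm, n = 85 / 116 | Power, n = 85 / 116 | n per arm for 80% power |
|---|---|---|---|
| 0.5% | 0.4 / 0.6 | 6% / 6% | 4,673 |
| 1% | 0.9 / 1.2 | 8% / 9% | 2,319 |
| 2% | 1.7 / 2.3 | 12% / 14% | 1,141 |
| 5% | 4.3 / 5.8 | 23% / 30% | 435 |

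With so few expected events the approximation is rough, but the message is clear: this trial can put a limit on wound harm and cannot test for it.

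**The case against.** The documents are not silent on safety. Any adverse event is reportable, serious ones go to the ethics board, and a committee reviews safety. Section 11.1 refers to a case report form tied to visits; that form is not in the documents, and the committee charter and a fuller SAP are still to be written. The list in 7.3 is not presented as exhaustive. A wound event could surface in a free-text answer or a spontaneous report and be tabulated by arm after unblinding. This stands to the extent that one cannot say the trial will have no comparative information at all. It does not supply systematic ascertainment, and a later SAP cannot analyse events that nobody looked for.

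A reader might infer more than the documents support:
- **That a pain difference could not be interpreted without complication data.** Complications after randomisation are part of each technique's effect on pain. The randomised comparison stays valid; complication data would help to explain it.
- **That section 2 would declare a technique superior overall.** Its sentence is limited to recovery, analgesia duration and quality of life.
- **That no technique may be called superior on pain without a complication table.** At 6–30% power such a table could not settle the matter, so it is no basis for a publication condition.
- **That the arms differ in strength.** No passage says so; all three use a continuous closure with the same suture material.
- **That women with complications will be dropped.** Only a literal reading of 5.4 leads there, and the synopsis points to past history.

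**Conclusion.** The point holds as a gap in planned ascertainment and reporting. The protocol names dehiscence as the risk that closure methods are meant to reduce, and lists four relevant complications. It describes no active way to find them after surgery and no comparison of them by arm. A closure could be favoured on pain with only incomplete spontaneous reports on wound harm. The disagreement between 5.4 and the synopsis must also be resolved, because one reading removes the very women who should be counted.

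What can be gained is modest. With full ascertainment and zero events, the upper limit is about 2.5% for roughly 117 women in an arm. Power for a doubling is about 6–30% over assumed rates of 0.5–5%. The conclusion does not depend on those rates; it rests on the data collection described and assumes that the unseen case report form adds no structured wound item. The change should be made, and is best made before recruitment, because events not sought at the time may not be fully recoverable later.

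**What to change.** 1. **Section 7.3:** add a chart review at 10 weeks for every randomised woman, and after withdrawal only as far as consent allows. Record the four listed complications and wound-related readmission, with dates. Staff blinded to arm should extract it without access to the operative record.
2. **Appendix C:** add one yes/no item, ahead of the three opening questions that can end the form, on wound problems, readmission or further surgery. This helps to catch events treated elsewhere.
3. **Sections 3.2 and 10.2:** name these events as a descriptive safety outcome, with counts and exact confidence intervals by allocated arm.
4. **Section 5.4 item 6 and the synopsis:** reconcile the two wordings, and state that women who have these events after surgery stay in the analysis in their allocated arm.

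**Cost.** A protocol amendment, possibly changed consent wording, one short extra chart extraction per woman and one questionnaire item. No procedure is added. Later notes, for example after a re-operation, may partly unblind the extractor. Intervals will be wide, and the report should say that the table bounds harm and does not test it.

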## 8 WITHDRAWAL OF SUBJECTS FROM THE STUDY

A subject may be withdrawn from the study at any time if the subject, the investigator, or the Sponsor feels that it is not in the subject's best interest to continue.

All subjects are free to withdraw from participation at any time, for any reason, specified or unspecified, and without prejudice.

Reasonable attempts will be made by the investigator to provide a reason for subject withdrawals. The reason for the subject's withdrawal from the study will be specified in the subject's source documents.

Subjects who withdraw from the study will not be replaced.

## 9 DATA SAFETY MONITORING

Sunnybrook Health Sciences Centre Data Safety Monitoring Board (DSMB) will establish a Data Monitoring Committee (DMC) to review data related to safety and efficacy, to ensure scientific validity and merit of the study, according to Sunnybrook Health Sciences Centre Data Safety Monitoring Board Operations Manual and a DMC Charter to be established for this protocol.

## **10** STATISTICAL METHODS AND CONSIDERATIONS

Prior to the analysis of the final study data, a detailed Statistical Analysis Plan (SAP) will be written describing all analyses that will be performed. The SAP will contain any modifications to the analysis plan described below.

#### **10.1** Demographic and Baseline Characteristics

The following demographic variables will be collected through a chart review: age, gravida and para status, total number of previous CS, medical history, surgical history, ethnicity, obstetrical history, current obstetrical complications in this pregnancy, medications, height, and weight.

#### **10.2 Statistical Analysis**

For our primary outcome measure, we aim to perform statistical analysis using IBM® SPSS® Version. 26 Statistics Software for Windows to perform a two-sided T-test whereby comparing groups directly. Based upon an 80% power at an alpha of 0.05, we anticipate a 15% when comparing group 1 vs 2 and group 1 vs 3, we require a sample size of 255 participants across all three groups.

Specific to our subgroup analysis evaluating primary vs. repeat caesarean section, based upon an 80% power at an alpha of 0.05, we anticipate a 15% difference in comparing these two groups using a two-sided T-test. As a result, we require a sample size of 140 participants across these two groups.

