#### 5.2 Sample Size

Our sample size is based upon a power of 80% at an alpha of 0.05 based on a two-sided t-test comparing groups. Based on these findings, our total sample size in each arm is 85 participants. In total, as there are three arms, our total sample size requires 255 participants, whereby randomising 85 participants to each group. In addition, we aim to undertake a sub-group analysis comparing primary to repeat Caesarean section with a power of 80% at an alpha of 0.05. Once again, a two-sided t-test would be used and based on these findings, we would require a total sample size of 140 participants, whereby comparing 70 participants per group. Given these minimum requirements and we estimate a drop-out rate of approximately 35%, we aim to recruit a total of 350 participants to this study.

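### The operating surgeon is not listed for collection, is not a randomisation factor and is not in the analysis: a modest loss of precision and no planned check by operator, cheap to put right

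*Combined protocol and SAP*

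**What the plan says.** - **Analysis.** For the primary outcome, 10.2 intends "to perform a two-sided T-test whereby comparing groups directly". The comparisons are group 1 with 2 and group 1 with 3. Neither 10.2 nor the synopsis names a covariate, stratum or random effect.
- **Data collected.** Section 10.1 reads "The following demographic variables will be collected through a chart review: age, gravida and para status, total number of previous CS" and goes on with further characteristics of the woman. The list in 7.3 is of the same kind. Surgical history, where it appears, is the patient's. The Appendix C questionnaire has no item on the surgeon.
- **Allocation.** Section 7.1 describes an Excel-generated 1:1 scheme across the three groups and mentions no stratification.
- **Surgeon.** The operating surgeon is mentioned only in 7.2: "The operating surgeon will be informed which method of fascial closure will be undertaken". The same section bars these surgeons from collecting outcome data.
- **Reason to expect variation.** Section 2 remarks that "much of the development of surgical approaches for trainees is based on the centre at which they are trained" and that no approach is standard.
- **Later plan.** Section 10 promises a detailed SAP before the final analysis, which may modify the methods.

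**The concern.** In a trial of surgical technique, the person closing the fascia is part of how the intervention is delivered. The hypothesis in 2.1 turns on the bulk and position of the knot, which are in the surgeon's hands. Women operated on by the same surgeon may therefore have more similar pain scores than women operated on by different surgeons. A two-sample t-test leaves that shared component in the error term.

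Three things are at stake, all modest:
- power that could be recovered at almost no cost;
- a table showing whether each surgeon's cases fell evenly across the arms;
- an estimate of whether the closure effect is consistent across operators, which matters to a unit elsewhere that is deciding whether to adopt a technique.

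The later SAP can add a model term, but only if the variable has been recorded.

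**Working it through.** **Inputs from the protocol.** Section 5.2: "Our sample size is based upon a power of 80% at an alpha of 0.05 based on a two-sided t-test comparing groups", and "our total sample size in each arm is 85 participants". Section 10.2: "we anticipate a 15% when comparing group 1 vs 2 and group 1 vs 3".

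**Inputs assumed.** The surgeon's share of pain variance (ICC) is taken as 0 to 0.15 and the number of surgeons as 6 to 20. The protocol gives neither.

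**Step 1: the planned 85 per arm.** No mean or SD is stated, so 85 can be neither reproduced nor refuted. It can only be solved backwards:

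d = (1.960 + 0.842) × √(2/85) = 0.430

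A 15% difference then requires an SD of 0.15/0.430 = 0.349 of the mean.

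**Step 2: most that adjustment can gain.** If all surgeon variance is removed at no cost, the residual SD becomes √(1 − ICC), and

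power = Φ( 0.430 / [√(1 − ICC) × √(2/85)] − 1.960 )

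| ICC | Power at 85 per arm | Per arm for 80% power, 85 × (1 − ICC) rounded up |
|---|---|---|
| 0 | 80.0% | 85 |
| 0.02 | 80.8% | 84 |
| 0.05 | 82.0% | 81 |
| 0.10 | 84.0% | 77 |
| 0.15 | 86.0% | 73 |

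These are upper limits, because estimating surgeon effects uses up some information.

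**Step 3: is the planned t-test valid?** In simulations of 85 against 85 individually randomised women (4,000 runs per setting, ICC 0 to 0.10, 10 or 20 surgeons, common closure effect), its two-sided type I error was 4.3% to 5.7%. Two simulation standard errors are 2 × √(0.05 × 0.95/4000) = 0.7 points, so this is consistent with 5%.

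**Step 4: fixed or random surgeon effects?** Fixed effects can lose power. With 20 surgeons and ICC 0.05, power was 76.9% against 79.2% for the t-test; with 10 surgeons and ICC 0.10 it was 82.3% against 80.3%. A REML random intercept did not show this loss:
- 20 surgeons, ICC 0.05: 80.6% against 79.6%;
- 10 surgeons, ICC 0.10: 83.0% against 80.2%;
- ICC 0: within 0.2 points of the t-test.

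Its type I error was 4.7% to 5.7%.

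**Step 5: if the closure effect itself varies between surgeons.** Let that effect have SD τ (in pain SDs) across S surgeons with equal caseloads. For inference to surgeons in general, the correct standard error exceeds the t-test's by the factor √(1 + (τ²/S)/(2/85)):
- S = 15, τ = 0.1: √(1 + 0.000667/0.02353) = 1.014. The t-test's SE is 1 − 1/1.014 = 1.4% too small, and the error rate is 2 × (1 − Φ(1.960/1.014)) = 5.3%.
- S = 6, τ = 0.2: √(1 + 0.006667/0.02353) = 1.133. The SE is 11.7% too small and the error rate is 8.4%.

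A random intercept does not change this. With S = 6, τ = 0.2 and ICC 0.05, simulated rejection was 8.5% for the t-test and 8.4% with the intercept.

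**The case against.** The strongest reply is that individual randomisation already deals with the surgeon. Technique is independent of operator in expectation, and chance imbalance is part of what the 5% error rate allows for. This stands. A reader might infer that a closure result could not be told apart from who operated; the individual allocation in 7.1 does not support that.

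A reader might also take 5.3% to 8.4% as the trial's true error rate. It is not. Those figures apply only to conclusions about surgeons beyond those taking part, and only if the closure effect varies between surgeons around an average of zero. If closure makes no difference in any surgeon's hands, there is no such variation and the error is nominal.

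Three further points stand in part:
- Section 2 speaks of differences between training centres, not between operators in this unit. The trial has one site, and section 6 describes common sutures and steps. The protocol therefore suggests that surgeons may vary but does not show it, and it does not say how many operate.
- The lists in 7.3 and 10.1 cover demographic items and need not be the whole case report form. The surgeon could presumably be retrieved from operative records, and the SAP could add the term. But nothing plans for this, and an adjustment chosen after the data have been seen carries less weight.
- The gain in power is small. At an ICC of 0.02 to 0.05 it is at most 1 to 2 points.

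**Conclusion.** The omission is confirmed: the surgeon is not among the listed data items, not a randomisation factor and not in the analysis. The planned comparison is still unbiased, with nominal error under a common closure effect.

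The cost is some precision, worth at most 2, 4 or 6 points of power at ICCs of 0.05, 0.10 or 0.15, together with no planned check of surgeon balance or of consistency across operators. These figures rest on assumed ICCs and on the standardised difference of 0.430 implied by 85 per arm. Rate this as a cheap, optional improvement.

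**What to change.** 1. Add to 7.3 and 10.1 a coded identifier and grade (staff or trainee) for whoever closes the fascia. This is the time-critical part.
2. In 10.2, estimate group 1 v 2 and group 1 v 3 from a linear model with arm as a fixed effect and surgeon as a random, not fixed, intercept.
3. Tabulate surgeon by arm.
4. As a sensitivity analysis, add an arm-by-surgeon random effect, and base any conclusion beyond these operators on it. The random intercept alone does not widen the standard error for that purpose.

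The cost is one coded field from the operative record and one model term. The code does not reveal the arm. The main limit is that surgeons with few cases contribute little information, so the arm-by-surgeon variance may be poorly estimated.

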## 7 STUDY TREATMENTS

#### 7.1 Method of Assigning Subjects to Treatment Groups

Up to 350 eligible patients will be randomly assigned to one of the three intervention groups in a 1:1 ratio using an Excel-based computer-generated randomisation scheme.

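### Pain is scored five times with about 35% drop-out expected, but the plan names only a t-test and no missing-data method; a repeated-measures model would use the scores that a late-visit t-test ignores

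*Combined protocol and SAP*

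**What the plan says.** Section 10.2 says the primary analysis will "perform a two-sided T-test whereby comparing groups directly", and gives the effect as "we anticipate a 15% when comparing group 1 vs 2 and group 1 vs 3". The synopsis names the same two contrasts for analgesia use and pain scores.

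Section 7.3 schedules the questionnaire for "post-operative day #1 and 2, and at 2, 6 and 10 weeks post-operatively", which is five scores per woman. The synopsis defines the pain endpoint over the whole 10 weeks, without a primary visit. Appendix C has four 0-10 pain ratings (worst, least, average, now), and none is chosen as primary.

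Section 5.2 states "our total sample size in each arm is 85 participants" and "we estimate a drop-out rate of approximately 35%, we aim to recruit a total of 350 participants". Section 8 says that withdrawals are not replaced.

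The documents give no summary measure, repeated-measures model, analysis set, missing-data rule or sensitivity analysis. Section 10 defers detail to a later SAP, which will record any changes to the analysis described there. Until then the t-test is the default.

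**The concern.** A t-test needs one number per woman. If that number is the week-6 or week-10 score, a woman who stopped answering contributes nothing, although her day 1, day 2 and perhaps week 2 scores are on file.

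Two things are at stake. One is precision, because about a third of the women may have no late score. The other is bias. Section 2.1 hypothesises that the closures differ in pain. If they do, and women with higher earlier scores are more likely to stop, the higher-pain arm loses more of its high scorers. The late comparison among responders then understates the difference the trial is looking for.

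A likelihood-based repeated-measures model uses the earlier scores and corrects this when drop-out depends only on scores already seen. The point is therefore partly an omission and partly a choice of method: a better one is available for the same data.

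**Working it through.** **1. The plan's own figures.** Section 5.2 gives a "power of 80% at an alpha of 0.05 based on a two-sided t-test comparing groups", with 85 per arm and 350 recruited. No SD or control mean is given, so 85 cannot be rebuilt forwards. Solving backwards:

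- n per arm = 2(1.960 + 0.842)² / d², so d = √(2 × 7.85 / 85) = 0.43 SD.
- 350 appears to come from 255 × 1.35 = 344. Allowing for 35% loss needs 255 / 0.65 = 392.3, so 393.
- 350 × 0.65 = 227.5 women remain, or 75.8 per arm.
- Power = Φ(d√(n/2) − 1.96). With 75.8 per arm: Φ(0.43 × 6.158 − 1.96) = Φ(0.688) = 75.4%. With all 116.7 per arm: Φ(0.43 × 7.638 − 1.96) = Φ(1.324) = 90.7%.

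So a late-visit t-test on responders has about 75% power even if drop-out is unrelated to pain.

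**2. Simulation set-up.** Two arms of 117 (350 / 3), five visits, multivariate-normal scores, monotone drop-out of about 35%, a true difference of 0.43 SD at every visit, and 1,500 runs per setting. The correlation between visits is an assumption, ranged from 0.3 to 0.85. It was either the same for all pairs of visits (exchangeable) or decaying with distance (AR(1)). The week-10 t-test on responders was compared with the maximum-likelihood repeated-measures contrast (arm-specific visit means, unstructured covariance).

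**3. Random drop-out spread over the visits.** Week-10 power is about 91% with no drop-out and about 75% with the t-test. The share of lost precision recovered is (Var of t-test − Var of model) / (Var of t-test − Var with no drop-out). For example, with AR(1) at 0.5 it is (0.1596² − 0.1576²) / (0.1596² − 0.1279²) = 0.00063 / 0.00911 = 7%.

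| Correlation | Model power, exchangeable | Recovered | Model power, AR(1) | Recovered |
|---|---|---|---|---|
| 0.3 | 74% | 13% | 75% | 2% |
| 0.5 | 80% | 33% | 78% | 7% |
| 0.7 | 84% | 61% | 80% | 27% |
| 0.85 | 88% | 73% | 84% | 47% |

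These values carry Monte Carlo noise, which is why the first row shows no gain in power. Recovering more than half needs a correlation of roughly 0.6 or more with the exchangeable pattern.

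**4. Drop-out depending on the previous pain score.**

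- *Same rule in all arms, no true effect:* no bias, and type I error stays at 5%.
- *Same rule, true effect 0.43 SD:* the t-test estimate shrinks by 0.01 to 0.08 SD, about 3% to 19%. Its power is 64% to 76%, against 74% to 90% for the model. For example, with AR(1) at 0.7 the shrinkage is 0.038 / 0.43 = 9%, and power is 70% against 79%.
- *Opposite rules by arm (logit slope +1 against −1 per SD, deliberately extreme), no true effect:* the t-test shows a false difference of 0.10 to 0.61 SD, with type I error of 9% to 98%.
- The model's estimate was within about 0.01 SD of the truth throughout.

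**5. The questionnaire's skip rule.** In Appendix C, three No answers (no unusual pain today, no pain medication in the last 7 days, no daily need for medication) end the form before any 0-10 item. These blanks depend on current pain, so the model does not correct them. In an illustration assuming that 20% or 40% of the reference arm skip at week 10, with correlations of 0.4 to 0.8, treating skips as missing moved the model estimate from 20% too small to 26% too large. A simple comparison scoring them as 0 stayed within about 3% of the truth.

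**The case against.** The strongest reply is that the plan does not prescribe the analysis being criticised. A reader might infer separate t-tests at each questionnaire, run on whoever replied. Section 10.2 does not say this, and the synopsis describes results over 10 weeks. A t-test on each woman's mean or area under the curve fits the text as well and would use early scores. This stands as a reading of the text, but it does not remove the problem. For a woman with missing visits, such a summary must either drop her or average whichever visits she answered, which mixes early and late pain.

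A second reply is that the later SAP will settle missing data. That is the proper place for it, but nothing in Section 10 commits to a change.

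A third is that the bias is limited. This is right. It would be wrong to infer that any link between pain and drop-out biases the comparison: under a common rule with no true effect there is none. Large bias needs rules that differ by arm, and Section 7.2 makes that less likely because patients are to be blinded and the operating surgeon does not collect outcomes.

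The model's advantage also rests on assumptions. The effect size is back-solved, it is held constant over visits, and the simulated scores are normal. Real week-10 scores may pile up near 0.

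**Conclusion.** The point holds as a moderate one. With five scores per woman and about 35% expected loss, naming only a t-test leaves missing pain scores without a plan, and at a late visit it would ignore data already collected. When drop-out follows earlier pain and the closures differ by an assumed 0.43 SD, the cost is a shrinkage of about 3% to 19%. Under random drop-out the cost is reduced precision only.

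A reader might infer that a repeated-measures model recovers most of the lost precision. The documents cannot support that, because they give no between-visit correlation; over the assumed range the share runs from about 2% to 73%. The more dependable gain is freedom from bias when drop-out depends on observed scores.

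Part of the gap between 75% and the planned 80% comes from how 350 was derived, not from the choice of test. The 72-hour analgesia endpoint closes before the week-2 questionnaire and is largely untouched.

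**What to change.** In Section 10.2, or in the SAP before any outcome data are seen:

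1. Name one 0-10 rating and one primary visit.
2. Score the 0-10 items as 0 when a returned questionnaire was ended by the three No answers. Keep these women distinct from those who returned nothing.
3. Replace the pain-score t-test with a mixed model for repeated measures on all observed scores, with arm, visit, arm-by-visit and primary/repeat status as fixed effects and an unstructured covariance. Read the 1 vs 2 and 1 vs 3 contrasts at the primary visit.
4. Add a sensitivity analysis that imputes scores for true non-responders and shifts them over a stated range in both directions, since women may stop because they are worse or because they have recovered.

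The cost is SAP wording and some analysis time, with no new data. The downside is that the model assumes missing scores are predictable from observed ones, which step 4 probes but cannot verify. Scoring skips as 0 is a convention, because the first gate question sets aside everyday pain; the SAP should say so.
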